11.7.3. Angiography-derived coronary physiology

Coronary physiology measurements during emergency PCI can be used to assess the coronary microvascular function which is affected amongst other factors by the pre-stenting thrombotic burden and distal embolisation of atherothrombotic material during angioplasty.³ Indeed, coronary physiology measurements under adenosine-induced hyperaemia can be employed to characterise microvascular obstruction and predict the extent of myocardial infarction.²¹ Contemporary work enables us to derive cardiac physiology indices such as quantitative flow ratio non-invasively using coronary angiograms.^{22,23}

11.7.4. Extracted Thrombus Imaging

Intracoronary thrombus/plaque material obtained with the use of aspiration/stent-retriever thrombectomy as part of the procedure will be imaged *ex-vivo*. Images will be obtained in the catheterisation laboratory and stored in a pseudonymised format. The extracted thrombus will not be stored by the study team and will be discarded.

11.7.5. Electrocardiography (ECG)

ECG refers to the measurement of the electrical activity of the heart. It is a routine non-invasive assessment carried out in patients with suspected or known coronary artery disease.

11.8. Subsequent telephone follow-ups

Participants will have a scheduled telephone follow-up 6 months after their randomisation to the study. This telephone follow-up will gather information on concurrent medication therapy, patient reported outcomes, study outcomes and serve as an opportunity to log a participant's recovery progress.

11.9. Definition of End of Trial

Recruitment to the trial will cease as soon as 81 participants have been randomised in the study and have completed follow-up at 6 months. The trial will end when the last patient exits the study. To ensure that

Date and version No:22/04/2024 v4.0

the scientific integrity of the trial is maintained, should the target recruitment not be reached by the pre-specified study end-date we will seek an extension of the study

12. IDENTIFICATION & DESCRIPTION OF THE INVESTIGATIONAL DEVICE & COMPARATORS

12.1. Investigational Device & Comparators

12.1.1. Standalone PCI (Arm 1)

Participants randomised to the standalone PCI arm of the RETRIEVE AMI trial will have standard of care treatment. Participants will undergo PCI with devices and techniques driven by clinical decision making at the patient level and institutional level, and carried out in accordance with local guidelines.

Commented [FK(03]: This should be made applicable to both organisations so perhaps "carried out in accordance with the hospital department guidelines."

Commented [RK4R3]: Thank you. Addressed.

12.1.2. Aspiration thrombectomy and PCI (Arm 2)

Participants randomised to Arm 2 of the RETRIEVE AMI trial will have standard of care treatment with manual thrombectomy catheter and PCI. Participants will undergo PCI with devices and techniques driven by clinical decision making at the patient level and institutional level, and carried out in accordance with local guidelines.

12.1.3. Investigational arm (Arm 3)

Participants randomised to the stent-retriever thrombectomy arm of the RETRIEVE AMI trial will undergo stent-retriever thrombectomy with the Solitaire™ X Revascularisation Device (Figure 3). The Solitaire™ X revascularisation device has been clinically approved and CE marked for use in acute ischaemic stroke endovascular intervention.¹⁴ Solitaire™ X works by mechanically retrieving the thrombus and restoring blood flow to the area distal to the occlusion. The Solitaire™ X Revascularisation Device is a self-expanding stent designed for dynamic clot integration with radiopaque markers that enhance visualisation of the optimal working length. Features including the range of stent diameters and usable lengths are presented in Appendix B. The device can be used in

vessels with a diameter between 2.0mm and 5.5mm at the thrombotic occlusion site (Appendix B).

Figure 3: Solitaire™ X device

After a thrombotic occlusion has been identified and crossed with a guidewire, the stent-retriever thrombectomy proceeds as described below (see Appendix C for schematic diagram).¹⁵ A microcatheter (e.g. PhenomTM, MarksmanTM) is advanced over the guidewire. Once the microcatheter has traversed the thrombotic occlusion the SolitaireTM X revascularisation device is advanced through the microcatheter until the usable length of the stent extends past each side of the thrombus in the vessel. Then the microcatheter is retracted to the proximal radiopaque marker of the stent. As this retraction occurs the stent self-expands and entangles the thrombus. Finally, the microcatheter and SolitaireTM X Revascularisation Device are withdrawn as a unit under continuous aspiration into the guide catheter. PCI will then proceed with devices and techniques driven by clinical decision making at the patient level and institutional level, and carried out in accordance with local guidelines.

12.1.4. Masking (blinding)

Due to the interventional nature of the trial, masking is not applicable.

Commented [FK(07]: This should be made applicable to both organisations so perhaps "carried out in accordance with the hospital department guidelines."

Commented [RK8R7]: Addressed.

12.1.5. Storage of investigational devices

The SolitaireTM X Revascularisation Device and Phenom microcatheters will be provided by Medtronic. The OFDI catheters will be provided by Terumo Inc. We will be documenting the number of devices, with their lot numbers, that will be shipped to the John Radcliffe Hospital and Newcastle Upon Tyne Hospitals NHS Foundation Trust. After their delivery, the kit will be stored in designated spaces at both sites and kept in a cool, dry place. We will document on the CRF the LOT number and expiry date for each device for each patient.

12.2. Retriever thrombectomy safety

Stent-retriever thrombectomy is clinically tested and licensed for endovascular intervention in acute ischaemic strokes with large vessel occlusions involving the internal carotid and the first segment of the middle cerebral artery.^{14,24} Our proposed pilot in acute coronary syndrome – STEMI patients would therefore represent an off-license application for the SolitaireTM X Revascularisation Device. Endovascular intervention for acute ischaemic stroke bears similarities to coronary intervention for acute myocardial

Clinical Trial Protocol Template version 15.0

CONFIDENTIAL

© Copyright: The University of Oxford and Oxford University Hospitals NHS Foundation Trust 2019

Page 29 of 57

Date and version No:22/04/2024 v4.0

infarction. Off license use of retriever thrombectomy in STEMI patients is reported twice in the literature with no reported complications and a successful recanalization outcome.^{15,16}

From an anatomical perspective, the Solitaire™ X revascularisation device is licensed for interventions in vessels with a minimum diameter of 2mm and a maximum of 5.5mm depending on the device model used (see appendix A). The diameter of internal carotid and middle cerebral arteries (arteries for which Solitaire™ X intervention is licensed) is reportedly 3.38 ± 1.34 mm and 2.45 ± 0.85 mm respectively.²⁵ Our pilot study is designed to include patients with heart attack due to thrombotic occlusion of a “large caliber” coronary artery (diameter at the site of occlusion ≥ 3.0 mm). The size range of the target vessel is thus well within the safety range proposed by the manufacturer (e.g. between 2.0 and 5.5 mm).

From a device perspective, in stroke patients Solitaire™ X revascularisation device failure was reported in one case (0.8%) in the two pivotal trials that examined this end-point with no significant sequelae.^{14,26} Regarding device related complications in patients randomised to the Solitaire™ X revascularisation device, arterial dissection or perforation was reported in 5/211 (2.3%). Perforations, albeit in the coronaries are encountered in routine PCI practice in 0.37% of patients²⁷, while edge dissections following stent deployment in 7.7% of patients.²⁸ The relatively higher perforation with the Solitaire™ X device can be explained by the tortuosity of the intracerebral vessels that are treated as well as the early stage of the thrombectomy experience in the RCTs and the small sample size. To minimise the potential for coronary perforations in our trial, we will include patients with thrombotic occlusions involving the right coronary artery prior to the crux, e.g. in a vessel segment with minimal, if any, tortuosity. Nonetheless, in the event of a coronary perforation the treatment – angioplasty – is similar to the definitive treatment for the myocardial infarction.

Finally, stroke in the context of pPCI is reported in 0.25% to 0.5% of STEMI cases²⁹⁻³¹ and in ~0.8% of STEMI patients with aspiration thrombectomy and PCI.³⁰ In the Solitaire™ X device trials, the rate of embolisation to vascular fields proximal to the target vessel is not reported. It is therefore not possible to estimate the risk of stroke for our trial. However, from a mechanistic perspective stent-retriever thrombectomy is based

Date and version No:22/04/2024 v4.0

on the concept of integration of the stent scaffold into the thrombus which in combination with the withdrawal of the stent into the microcatheter and the continuous aspiration on withdrawal renders embolisation of thrombotic material less likely.

12.3. Other Interventions

Not applicable

13. SAFETY REPORTING

13.1. Definitions

Adverse Event (AE)	Any untoward medical occurrence, unintended disease or injury or any untoward clinical signs (including an abnormal laboratory findings) in participants, users or other persons whether or not related to the investigational medical device. This includes events related to the investigational device or comparator, events related to the procedures involved (any procedure in the protocol). For users or other persons this is restricted to events related to the investigational medical device.
Adverse Device Effect (ADE)	An adverse event related to the use of an investigational medical device. This definition includes any events resulting from insufficient or inadequate instructions for use, deployment, implantation, installation, or operation, or any malfunction of the investigational device. This definition also includes any event resulting from user error or form intentional misuse of the investigational device.
Serious Adverse Event (SAE)	Any untoward medical occurrence that: 
• Results in death• Is life-threatening,• Requires inpatient hospitalisation or prolongation of existing hospitalisation,• Results in persistent or significant disability/incapacity, or• Is a congenital anomaly/birth defect.• Other important medical events.


Included herein are device deficiencies that might have led to a serious adverse event if:
 
a) suitable action had not been taken or
 
b) intervention had not been made or
 
c) circumstances had been less fortunate.
 
These are handled under the SAE reporting system.
 
Planned hospitalisation for a pre-existing condition, or a procedure required by the trial protocol, without serious deterioration in health, is not considered a serious adverse event.
 
The term 'life-threatening' in the definition of 'serious' refers to an event in which the patient was at risk of death at the time of the event. It does not refer to an event that hypothetically might have caused death if it were more severe.
 
Hospitalisation for a pre-existing condition, including elective procedures planned prior to study entry, which has not worsened, does not constitute a serious adverse event.
 
Other events that may not result in death, are not life threatening, or do not require hospitalisation, may be considered a serious adverse event when, based upon appropriate medical judgement, the event may jeopardise the patient and may require medical or surgical intervention to prevent one of the outcomes listed above.
	
---	--

Serious Adverse Device Effect (SADE)	
Any untoward medical occurrence that can be attributed wholly or partly to the device, which resulted in any of the characteristics of a serious adverse event as described above.
 
Unanticipated Serious Adverse Device Effects (USADE)
 
Any serious adverse device effect which, by its nature, incidence, severity or outcome, has not been identified

Device deficiency	
Inadequacy of a medical device with respect to its identity, quality, durability, reliability, safety or performance. Device deficiencies include malfunctions, use errors and inadequate labelling.
 
Device deficiencies that did not lead to an adverse event, but could have led to a medical occurrence if suitable action had not been taken, or intervention had not been made or if circumstances had been less fortunate

User error	
Act or omission of an act that results in a different medical device response than intended by the manufacturer or expected by the user.
 
Use error includes slips, lapses and mistakes. An unexpected physiological response of the subject does not itself constitute a use error.

Severity definitions

The following definitions will be used to determine the severity rating for all adverse events:

Mild: awareness of signs or symptoms, that does not interfere with the subject's usual activity or is transient that resolved without treatment and with no sequelae.

Moderate: a sign or symptom, which interferes with the subject's usual activity.

Severe: incapacity with inability to do work or perform usual activities.

Arterial injury classification scheme

Coronary dissections and perforations will be classified according to the established NHLBI and Ellis classification schemes.^{32,33} A significant coronary dissection is defined as a dissection leading to coronary flow impairment or coronary occlusion.

13.2. Causality

The relationship of each adverse event to the trial device may be determined by the manufacturer and/or a medically qualified Investigator according to the following definitions:

Not related: The event is clearly related to other factors such as the patients/participants clinical condition, therapeutic intervention, concomitant medication.

Unlikely: The event is probably produced by other factors such as the patients/participants clinical condition, therapeutic intervention, concomitant medication and does not follow a known response pattern to the device

Possibly: The event follows a reasonable temporal relationship from the time of placement/administration and/or follows a known response pattern to the device but could have been caused by other factors such as the patients/participants clinical condition, therapeutic intervention, concomitant medication.

Most probable: The event follows a reasonable temporal relationship from the time of placement/administration and/or follows a known response pattern to the device and could not have been caused by other factors such as the patients/participants clinical condition, therapeutic intervention, concomitant medication. Further the event immediately follows the administration/placement of the device and improves on stopping or removing the device.

13.3. Procedures for Recording Adverse Events

All adverse events (including ADEs) and device deficiencies occurring during the course of the study will be recorded on the CRF whether or not attributed to the trial device. The information recorded will include but not be limited to:

- A description of the event
- The dates of the onset and resolution
- Action taken
- Outcome
- Assessment of relatedness to the device
- Whether the AE is serious or not
- Whether the AE arises from device deficiency
- Whether the AE arises from user error

The severity of events will be assessed on the following scale: 1 = mild, 2 = moderate, 3 = severe.

The CI shall submit to Medtronic a report of AEs and ADEs that occur in Arm 3 of this study. AEs/ADEs considered related to the device as judged by a medically qualified investigator or the Sponsor will be followed either until resolution, or the event is considered stable.

It will be left to the Investigator's clinical judgment to decide whether or not an AE/ADE is of sufficient severity to require the participant's removal from treatment. A participant may also voluntarily withdraw from treatment due to what he or she perceives as an intolerable AE/ADE. If either of these occurs, the participant must undergo an end of trial assessment and be given appropriate care under medical supervision until symptoms cease, or the condition becomes stable.

13.4. Reporting Procedures for Serious Adverse Events

Reporting of all Serious Adverse Events will be done in accordance with the European Commission Guidelines on Medical Devices Serious Adverse Event Reporting (MEDDEV 2.7/3; December 2010).

Date and version No:22/04/2024 v4.0

SAEs/SADEs that pose an immediate risk to patient health or safety will be reported to the trial TSG/Sponsor immediately or no later than 24 hours after the Investigator is aware and to the device manufacturer, the MHRA and the REC within 2 calendar days of the Chief Investigator becoming aware of the event. The SAE form should be emailed to [contact].

All other reported SAEs/SADEs will be reported to the trial TSG, the Sponsor, device manufacturer and the MHRA within 7 calendar days of notification, if appropriate. This will not include SAEs that may be expected as part of the risks of routine care. Adverse device events (SADEs, USADEs) and device deficiencies will also be reported to the device manufacturer. All SAEs will be followed up to resolution.

SAEs/SADEs will be recorded for a time period starting from verbal assent/investigational device deployment to 30 days following the use of the device.

13.5. Expectedness

Expectedness will be determined according to the Manufacturers risk analysis report

13.6. Trial cessation rules

The trial will be halted early if any of the following occur:

- >2 transient ischaemic attack /ischaemic stroke-related SADEs
- >2 coronary perforation-related SADEs
- > 2 significant coronary dissection-related SADEs

13.7. Safety Monitoring Committee – Trial Safety Group (TSG)

The Oxford University Hospitals Trust Trial Safety Group (TSG) will conduct a review of all SAEs/SADEs for the trial reported during the quarter and cumulatively. The aims of this committee include:

- To pick up any trends, such as increases in un/expected events, and take appropriate action
- To seek additional advice or information from investigators where required

- To evaluate the risk of the trial continuing and take appropriate action where necessary

13.8. Safety of stent-retriever thrombectomy

See Section 12.2.

13.9. Safety of intravascular imaging

Intravascular imaging using OCT is often performed during PCI to assist in the procedure. The utilization of this modality typically adds up to 5 minutes to the procedure duration. Use of any intra-coronary device including OCT can cause ischaemia, chest discomfort or, rarely, other local coronary complications during the PCI. However, this is in the context of a PCI procedure where significant interventions such as balloon expansion and stent deployment are already being carried out in the coronary artery, which themselves may cause ischaemia, chest pain that may require the use of analgesia, or other local coronary complications.

14. STATISTICS

14.1. Number of participants

Based on estimates from previously published work^{9,34} and our stipulation for inclusion of patients with high thrombotic burden, we anticipate a mean pre-stent thrombus volume of 9.6mm³ with a standard deviation estimate of 5.1 mm³ in the standard of care arms. Since this is the first pilot of stent retriever in acute coronary syndromes there is no previous published work that can inform on the expected pre-stent thrombus volume reduction with retriever thrombectomy. We have therefore hypothesised a 33% reduction in mean pre-stent thrombus volume. Using a 1-way pairwise ANOVA with a 2-sided equality, accounting for 2 pairwise comparisons with an α of 0.05, a sample size of 72 patients would have 80% power to detect a 33% reduction in pre-stent thrombus volume with retriever thrombectomy.³⁵ The approach that was used accounts for two pairwise comparisons. Indeed, for one such comparison a sample size of n=48 (n=24 for Arm 1 and 24 for Arm 3) would maintain the desired α of 0.05 and β of 0.2. Given that aspiration thrombectomy was not shown to differ from no thrombus modification,⁹ a sample size of n=48 (n=24 for Arm 2 and n=24 for Arm 3) would maintain the desired α of 0.05 and β of 0.2 for this comparison. The overall sample size is therefore increased by a further n=24 patients for the aspiration thrombectomy group. This leads us to n=72 patients required to show a 33% reduction in pre-stent thrombus burden with a power of 80%. Assuming 12.5% of patients will not have analysable OCT imaging, we plan to enrol 81 patients (n=27 in each group) to ensure the study remains adequately powered.

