14.2. Analysis of Endpoints

In keeping with our usual practice, we will obtain expert statistical advice from the Centre for Statistics in Medicine (or equivalent) for each specific task. A flow diagram detailing number of participants screened and randomised will be provided. Analysis of the OCT-derived primary and secondary endpoints (including angiography-derived) will be conducted offline in a blinded fashion. Summary statistics, including means, medians, and variances, will be calculated at each time point and for each type of data and group (e.g. baseline characteristics, parameters derived from OCT, angiography-derived coronary physiology). The distribution of the levels will be described. For each parameter an analysis of variance will be carried out.

An analysis evaluating for a between group difference in pre-stent thrombus volume will first use an 1-way ANOVA with a 2-sided equality test to assess for an overall trend. Post-hoc analyses exploring the following hypotheses i) retriever thrombectomy (Arm 3) is different to no thrombus modification (arm 1) and ii) retriever thrombectomy (Arm 3) is different to aspiration thrombectomy (Arm 2) will be performed using the Dunnett test. Control of the Type I error at 5% two-sided significance level due to multiple testing will be achieved using Dunnett's method.³⁶ Missing data for the primary analysis will be dealt with complete case analysis if data missingness is <10% (<3 cases per group). If missingness is higher, multiple imputation will be performed instead. Major adverse cardiac and cerebrovascular events will be analysed using proportions statistical testing (Fisher's exact or χ^2 tests), yet they represent an exploratory analysis.

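### Section 14.1 claims 80% power with 24 analysable patients per arm; its own inputs give about 46% per planned Dunnett comparison

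*Combined protocol and SAP*

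**What the plan says.** All the inputs are in section 14.1. For the control arms, "we anticipate a mean pre-stent thrombus volume of 9.6mm³" with a "standard deviation estimate of 5.1 mm³ in the standard of care arms". For the effect: "We have therefore hypothesised a 33% reduction in mean pre-stent thrombus volume". For the method: "Using a 1-way pairwise ANOVA with a 2-sided equality, accounting for 2 pairwise comparisons with an α of 0.05". The result is that "a sample size of 72 patients would have 80% power to detect a 33% reduction in pre-stent thrombus volume with retriever thrombectomy".

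The section builds up the 72 as follows: "for one such comparison a sample size of n=48 (n=24 for Arm 1 and 24 for Arm 3"), the same for Arm 2 against Arm 3, and hence 24 more patients for the third arm. It then allows for unusable imaging: "Assuming 12.5% of patients will not have analysable OCT imaging, we plan to enrol 81 patients", 27 per group, so that power is kept.

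Section 14.2 plans a one-way ANOVA of pre-stent thrombus volume, then Dunnett tests of Arm 3 against Arm 1 and Arm 3 against Arm 2. Its error statement reads: "Control of the Type I error at 5% two-sided significance level due to multiple testing". Neither section mentions a log scale, a baseline adjustment, a one-sided test or a smaller SD for Arm 3.

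**The concern.** A standardised effect of about 0.62 is moderate. Detecting it with 80% power in a two-sided, two-group comparison takes roughly 40 patients per group before any allowance for multiplicity, so 24 per group is too few on sight.

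Pre-stent thrombus volume is the primary efficacy outcome, and section 14.1 presents 81 patients as enough for adequate power. If real power is near one half, a true one-third reduction would be missed in a given comparison slightly more often than it is found. A reader who trusts the stated 80% would then take a non-significant result as fair evidence against an effect of that size. The type I error rate is not affected.

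**Working it through.** **Inputs (section 14.1).** Mean 9.6 mm³; SD 5.1 mm³; reduction 33%; two-sided α 0.05 with two comparisons; power 80%. The difference is 0.33 × 9.6 = 3.168 mm³ (3.2 mm³ if exactly one third). The standardised effect is 3.168/5.1 = 0.621. The SD is given only for the control arms; I apply it to Arm 3 as well, as a standard ANOVA and Dunnett test do.

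**Trying to reproduce the plan's 24 per arm.** For two means,

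n per arm = 2 × [(z₁₋α/₂ + z₀.₈) × SD/difference]²

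| α per comparison | n per arm, difference 3.168 | n per arm, difference 3.2 | Same, without the factor 2 |
|---|---|---|---|
| 0.025 (0.05 split over two) | 49.3 | 48.3 | 24.6 / 24.1 |
| 0.05 (no adjustment) | 40.7 | 39.9 | 20.3 / 19.9 |

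For example, at α = 0.025: 2 × [(2.241 + 0.842) × 1.610]² = 49.3.

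The formula does not return 24 per arm. The plan's numbers appear if the factor 2 for a difference between two means is left out at α = 0.025 (24.1 to 24.6). Put the other way, about 48 is the requirement for each arm, and section 14.1 uses 48 as the total for two arms.

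**Power at the planned size.** For Dunnett with two comparisons, 24 per arm and 69 error degrees of freedom, the two-sided 5% critical value is 2.258. The non-centrality is 0.621 × √(24/2) = 2.152. The non-central t distribution gives power of 0.462, and simulation agrees (0.462).

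| Analysis, 24 per arm | Power |
|---|---|
| Dunnett, each comparison (planned) | 46% |
| Dunnett, at least one significant | 62% |
| Dunnett, both significant | 30% |
| Omnibus F test (planned first step) | 58% |
| Unadjusted two-sided t-test | 56% |
| Unadjusted one-sided t-test at 5% | 68% |
| Arm 3 against Arms 1 and 2 pooled, two-sided t-test | 69% |

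With all 27 per arm analysable, Dunnett power is 51%. With 48, 49 and 50 per arm it is 79.0%, 79.9% and 80.8%.

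**What 24 per arm can detect with 80% power.** With Dunnett, a standardised effect of 0.897, which is 0.897 × 5.1 = 4.57 mm³, or 4.57/9.6 = 47.6%. Unadjusted, 4.21 mm³, or about 44%. For the 33% reduction to be detectable with Dunnett, the SD would have to be 3.168/0.897 = 3.5 mm³.

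**Allowance for unusable imaging.** 72 × 1.125 = 81, so the loss was added to 72 rather than divided out. Dividing gives 72/0.875 = 82.3. At 12.5% loss, 81 × 0.875 = 70.9 patients remain. The loss that leaves 72 is 1 − 72/81 = 11.1%.

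**The case against.** The strongest reply is that other assumptions bring 24 per arm closer to 80%. The SD is stated only for the control arms. If it shrinks in proportion to the mean (about 3.4 mm³ in Arm 3), normal-approximation power is about 61% at α 0.025 and 72% unadjusted; an unadjusted one-sided test then reaches 81%. On a log-normal scale an unadjusted two-sided test has about 79%, and about 71% at α 0.025. These figures are right, and they limit the conclusion to the plan as written. They do not rescue the claim: sections 14.1 and 14.2 specify two-sided pairwise tests on thrombus volume adjusted for two comparisons, and the variants near or above 80% drop at least one of those features.

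On multiplicity, adding 24 patients for a third arm does not raise the number in either comparison. It would be unfair, though, to say that the adjustment was ignored: the match to 24 arises at α = 0.025, which suggests that it was in the calculation. The factor-2 explanation remains an inference. The power figure does not depend on it.

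The trial is also labelled a device pilot and exploratory, and the 33% is openly a hypothesis. A pilot may be small, but a stated 80% power still has to be correct. Finally, the attrition slip is worth about one patient and is minor.

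**Conclusion.** The concern holds. The statement that 72 analysable patients give 80% power for a 33% reduction is wrong on the plan's own figures. Power is about 46% per planned Dunnett comparison at 24 per arm and 51% at 27, a shortfall of roughly 30 percentage points. This assumes normally distributed volumes with a common SD of 5.1 mm³ and equal means in the two control arms, which is how section 14.1 frames the calculation. No reading of the stated two-sided, adjusted, pairwise plan reaches 80%. The 12.5% imaging allowance is also slightly miscalculated, with negligible effect on power.

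**What to change.** Correct section 14.1 as follows:

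- State that 24 analysable patients per arm give about 46% power per Dunnett comparison for a 33% reduction, or 80% power for a reduction of about 48% (4.6 mm³), with a common SD of 5.1 mm³.
- Delete the statements that 24 against 24 keeps α at 0.05 and β at 0.2, and the closing claim of adequate power.
- State that 81 enrolled patients leave 72 analysable if up to 11.1% of imaging is unusable.
- Add that a non-significant comparison does not exclude a 33% reduction.

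The cost is a protocol wording change and a less favourable power statement. Enrolment need not change to make the text correct. For comparison, keeping the 80% claim for a 33% reduction would take about 50 analysable per arm (150 in total), or 150/0.875 = 171.4, so at least 172 enrolled (174 in equal arms of 58).

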9. TRIAL DESIGN

RETRIEVE AMI is an investigator-initiated, multi-centre, exploratory three arms, randomised controlled trial. Patients over the age of 18 admitted for primary PCI (pPCI) for ST elevation myocardial infarction and meeting the inclusion criteria laid out in section 10.2 will be 1:1:1 randomised to receive either standalone PCI (Arm 1), thrombus aspiration + PCI (Arm 2) or retriever thrombectomy + PCI (Arm 3). Recruitment is expected to last for 18 months with the study finishing when the last follow-up of the last recruited patient is completed and all data is entered into the study. Each participant is expected to remain in the study for 6 months during which one telephone follow-up at 6 months will be arranged. (Figure 1, Appendix A)

The RETRIEVE AMI will enrol specifically patients with

- evidence of large thrombus burden on coronary angiography
- with culprit lesion located in a relatively large caliber (diameter > 3.0 mm) coronary artery

By only including a large caliber vessel, the retriever-stent will be tested in a setting where the currently available technology is perceived to be suboptimal as described in section 6. Our decision to expand recruitment to the left coronary system was driven by our experience with the device in this trial as well as from published reports of the systematic evaluation of the NeVa (Vesalio) stent retriever device. Indeed, the authors have shown that thrombectomy is safe in both the left and right coronary artery systems.¹⁷ Procedurally, we are reducing the risk of a major interaction of the device by placing a coronary guidewire alongside the stent retriever allowing us to retain safe control of the vessel whilst the clot is retrieved.

[figure not shown]

Figure 1: Trial flow chart

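### Enrolling 81 does not keep the 72 evaluable patients that section 14.1 requires if 12.5% lack analysable OCT; it covers a loss of 11.1%, a shortfall of about one patient

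*Combined protocol and SAP*

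**What the plan says.** Section 14.1 (Number of participants) builds the sample size in three steps.

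- Per comparison: "for one such comparison a sample size of n=48 (n=24 for Arm 1 and 24 for Arm 3"), and likewise 24 against 24 for Arm 2 versus Arm 3.
- In total: "This leads us to n=72 patients required to show a 33% reduction in pre-stent thrombus burden with a power of 80" per cent.
- For loss of the primary measurement: "Assuming 12.5% of patients will not have analysable OCT imaging, we plan to enrol 81 patients (n=27 in each group"), with the stated purpose of preserving power.

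Section 9 allocates patients 1:1:1, so the arms are meant to be equal. The primary efficacy outcome is OCT thrombus volume before stenting (sections 4 and 8), so a patient without analysable OCT has no observed primary outcome.

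The total of 81 is repeated in the synopsis (section 4) and in the definition of the end of trial (section 11.9). Section 14.3 works with an arm of 27. No section gives the inflation formula or a source for the 12.5%.

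**The concern.** A loss allowance should leave the required number after the assumed loss has occurred. Here the assumed loss is a share of patients enrolled, so the surviving fraction is 0.875 and the required number has to be divided by it. The enrolment figure of 81 is too small for that: after the stated loss it falls just short of 72.

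What is at stake is the consistency of a headline number. The total of 81 appears in several places, fixes when recruitment stops, and will be carried into the trial report, where a reader can check it against 72 and 12.5% in one line. Section 14.1 offers over-enrolment as the protection for power, and that protection is slightly smaller than described.

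**Working it through.** **Inputs, all from section 14.1 except the allocation (section 9)**

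- Evaluable patients required: 72 in total, 24 per arm
- Assumed fraction without analysable OCT: d = 0.125
- Planned enrolment: 81 in total, 27 per arm
- Allocation: 1:1:1

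**Reproducing the plan's figure.** Two routes lead to it.

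- N × (1 + d): 72 × 1.125 = 81.0, and 24 × 1.125 = 27.0 per arm. Both are exact.
- n / (1 − d) per arm, rounded down: 24 / 0.875 = 27.43, cut to 27, giving 3 × 27 = 81.

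The exact match makes the first route the more likely one, but the document does not show which was used.

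**Evaluable patients left at the stated loss**

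- Total: 81 × 0.875 = 70.9, against 72 required (short by 1.1)
- Per arm: 27 × 0.875 = 23.6, against 24 required (short by 0.4)

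**Loss that 81 does cover**

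- (81 − 72) / 81 = 9/81 = 11.1%

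**Enrolment that would keep 72 at a 12.5% loss**

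- Total: 72 / 0.875 = 82.3, rounded up to 83
- Equal arms: 24 / 0.875 = 27.43, rounded up to 28 per arm, so 84. Check: 84 × 0.875 = 73.5, or 24.5 per arm.

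**Cost in power, accepting the plan's premise of 80% at 24 per arm**

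In the normal approximation for a two-sided test at 0.05, 80% power corresponds to a standardised effect of 1.960 + 0.842 = 2.802. It scales with the square root of the number per arm.

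- √(23.625 / 24) = 0.992
- 2.802 × 0.992 = 2.780
- 2.780 − 1.960 = 0.820, and the normal distribution function at 0.820 is 0.794

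Power falls from 80% to about 79.4%, a loss of about 0.6 percentage points.

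**Chance of reaching the target, with independent 12.5% loss (binomial)**

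| Enrolled | At least 72 evaluable in total | All three arms at least 24 |
|---|---|---|
| 81 (27 per arm) | 43% | 17% |
| 83 | 66% | not calculated |
| 84 (28 per arm) | 75% | 39% |

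The 84 row is the comparator. Even enrolment from the correct formula leaves at least one arm below 24 more often than not, because the formula targets the expected number and does not guarantee it.

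**The case against.** The other side has five points.

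- **The cause is not documented.** This stands. A reader might infer that the sponsor multiplied by 1.125 where division by 0.875 was needed. The exact match suggests it, but rounding 27.43 down gives the same 81, and section 14.1 shows no formula. Only the mismatch between 81, 12.5% and 72 is established, and it is the same by either route.
- **The effect is negligible.** This largely stands. The shortfall is about one patient in a trial that sections 4 and 9 describe as a pilot and exploratory, and the 12.5% is itself an assumption. It limits the weight of the point but does not make the sentence correct.
- **The low chances of reaching 72 or 24 per arm exaggerate the harm.** This stands if 43% and 17% are quoted alone. Beside 75% and 39% at 84, much of the apparent risk is ordinary variation in the number lost.
- **The 12.5% could be read as a share of the 72.** This does not stand. The sentence speaks of patients without analysable imaging, and these are among those enrolled. Nine lost out of 81 is 11.1%.
- **Multiple imputation covers the loss.** This does not stand as a rebuttal. Section 14.2 uses complete cases only when missingness is below 10%, so a 12.5% loss would trigger imputation and the analysis would not be a complete-case one on 71. Imputation does not restore OCT measurements that were never obtained, and section 14.1 relies on enrolling more patients to protect power.

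**Conclusion.** The statement in section 14.1 is wrong as written. At the stated 12.5% loss, 81 enrolled patients give about 70.9 evaluable (23.6 per arm), not 72 (24 per arm). The figure of 81 supports a loss of up to 11.1%. This rests on the plan's own three numbers and on reading the 12.5% as a share of those enrolled.

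The size is about one evaluable patient. The power cost of about 0.6 points rests on accepting 80% at 24 per arm.

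A reader might infer two stronger conclusions, and neither is supported.

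- *That the inflation step leaves the trial underpowered.* On the plan's own premise power is still about 79.4%; what is missed is the count of 72.
- *That the inflation step explains a much lower power.* Recomputing from the plan's mean of 9.6 mm³, SD of 5.1 mm³ and 33% reduction does give only about 56 to 58% at 24 per arm (two-sided 0.05, unadjusted). That comes from the base calculation of 24 per arm, which is a separate issue, and raising enrolment to 83 or 84 would not cure it.

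**What to change.** Keep 81 and reword the last sentence of section 14.1 in one of two ways:

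- say that 81 allows for up to 11% non-analysable OCT; or
- keep the 12.5% and say that about 71 evaluable patients (23 to 24 per arm) are then expected, slightly below the target of 72.

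The first is the shorter edit, but it sets the loss rate to fit 81, and the documents give no source by which to judge whether 11% is realistic. The second keeps the planned rate and states its consequence.

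Any power figure quoted in that sentence should come from the corrected base calculation, not from the present 80%. If the base number is revised, the new requirement should be divided by 0.875 and rounded up per arm. Multiplying by 1.125 would leave 1.125 × 0.875 = 0.984 of whatever base is used.

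The cost is one sentence that reads slightly less favourably. With 81 kept, sections 4, 11.9 and 14.3 need no edit, and enrolment, design and analysis do not change.
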